2.4 Study Method

In order to obtain information on Regulatory PMS data after-market launch, or delegate will create the Regulatory PMS contract with the relevant clinics/hospitals and the physician in charge of the survey shall implement this Regulatory PMS in subjects that receive MenACWY-CRM in the relevant hospital/clinic since the contract date until the number of contracted survey cases, without omission, is reached.

Overview of Study Design

This is a multicenter post marketing surveillance study to monitor the safety of MenACWY-CRM administered according to the prescribing information to 3,960 healthy subjects from 2 months to 55 years of age in Korea.

Subjects will be enrolled at the time of their visit to a participating clinic or hospital for vaccination with MenACWY-CRM according to the routine clinical care.

	CONFIDENTIAL :	Last Update Date
	THIS DOCUMENT AND INFORMATION CONTAINED HEREIN IS PROPRIETARY TO COMPANY AND IS NOT TO BE DISCLOSED WITHOUT THE WRITTEN PERMISSION OF COMPANY.	20-APR-2018
STATISTICAL ANALYSIS PLAN(V6.0)		

At Visit 1 (Day 1), after obtaining consent from the subjects or subjects’ parents/legal representative (and Assent Form, if required by the relevant IRB), the vaccination will be administered. Subjects will remain under observation for at least 30 minutes in the clinic after study immunization.

The subjects or subject’s parent/legal representative will be then instructed to complete the Diary Card daily, reporting local and systemic adverse events and all other AEs occurring within 7 days following immunizations, and medically attended AEs or SAEs occurring up to Day 29 within the surveillance period after each study vaccination.

Subjects will also be instructed to return the completed diaries to the study site at Day 29 as follows:

- During a visit at the study center or
- Using the provided pre-addressed stamped envelope (PASE).

At the investigator discretion, the subject or subject’s parent/legal representative will be reminded of the date of the study termination by a phone call at Day 29. If any clarification is required after Diary Card retrieval the site staff will follow up by phone, and any additional finding will be recorded on the subject’s medical record.

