 - Infants 2 to 6 months of age : Three doses of MenACWY-CRM, each of 0.5 ml, is to be given with an interval of at least 2 months; the fourth dose schedule be administered during the second year of life with an interval of at least 6 months after the third dose.
 - Infants 7 to 23 months of age : MenACWY-CRM is to be administered as two doses, each as single dose (0.5ml), with the second dose administered in the second year of life and at least three months after the first dose.
 - 2 to 55 years of age : MenACWY-CRM is to be administered as a single dose (0.5ml).
 - * The infant from 2 to 23 months of age may enroll at any point, in the vaccination series, including those subjects who may already initiated vaccination series. According to parental consents, these subjects may be followed up for 29 days within the surveillance period after subsequent vaccination(s) at the same study site.

Non-Safety per protocol set

Subjects excluded from safety per protocol set except for subjects who did not receive MenACWY-CRM and follow-up failure.

Based on rules for estimation of each number of safety evaluation cases, the following local regulation and Guideline on Standards for re-examination for new drugs, etc of MFDS, non-safety analysis set are excluded from the safety analysis set:

Guideline on Standards for re-examination for new drugs, etc (Chapter II, no. 3)

Patient Population for Surveillance:

- A) Patients planned to receive a drug under surveillance by investigator's medical judgment shall be subject.
- B) Subject who do not use within approved range shall not be included in the subject in principal.

However, if data of subject whose use is beyond approved range is collected, perform analysis as a separate item.

	CONFIDENTIAL :	Last Update Date
	THIS DOCUMENT AND INFORMATION CONTAINED HEREIN IS PROPRIETARY TO COMPANY AND IS NOT TO BE DISCLOSED WITHOUT THE WRITTEN PERMISSION OF COMPANY.	20-APR-2018
STATISTICAL ANALYSIS PLAN(V6.0)		

C) Describe actual selection methods of subject in detail.

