4.1 Safety Endpoints

Safety will be assessed after administration of study vaccine in terms of the number and percentage of subjects with:

- Local and systemic solicited adverse events reported from study Day 1 (day of vaccination) through study Day 7 post-vaccination;
- Unsolicited AEs reported from study Day 1 (day of vaccination) through study Day 7 post-vaccination;
- Medically attended AEs reported from study Day 1 to study termination (Day 29/early termination);
- SAEs reported from study Day 1 to study termination (Day 29/early termination).

5. Assessment Criteria

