6.2 Safety Analyses

The number of subjects of AE[†] and the number of AEs[†] incurred shall be calculated, the incidence proportion of AEs[†] and its 95% confidence interval will be calculated using the normal approximation on the safety set and safety per protocol set.

† AE : AE includes solicited and unsolicited AE (DAY 1-7), medically attended AE (DAY 1-29) and SAE (DAY 1-29).

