6.2.1 Adverse Events by Baseline Characteristics

AE[†]s (as described below) will be reported (n %) for the following baseline characteristics in the safety set and safety per protocol set :

- Age group (2-23 months, 2-10, 11-18, 19-34, 35-55, 55-64)
- Children group (<18, ≥18)
- Gender (male, female)
- Past diagnosis (yes, no)

	CONFIDENTIAL :	Last Update Date
	THIS DOCUMENT AND INFORMATION CONTAINED HEREIN IS PROPRIETARY TO COMPANY AND IS NOT TO BE DISCLOSED WITHOUT THE WRITTEN PERMISSION OF COMPANY.	20-APR-2018
STATISTICAL ANALYSIS PLAN(V6.0)		

- Temperature location (axillary, oral, rectal, ear)
- Administration site (left deltoid, right deltoid, left thigh, right thigh, other)
- Concomitant medication (yes, no)
- Kidney disorder (yes, no)
- Liver disorder (yes, no)
- Pregnancy (yes, no)
- Number of previous Menveo (0, 1, 2, 3)
- Study vaccination number (1, 2, 3, 4)

The n(%) of AEs[†] and its 95% confidence interval will be calculated using the normal approximation and analyzed using χ^2 - test. If more than 20% of expected frequencies of the cell counts are less than 5, Fisher’s exact test will be used instead of the chi-square test.

† AE : AE includes solicited and unsolicited AE (DAY 1-7), medically attended AE (DAY 1-29) and SAE (DAY 1-29).

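### SAP V6.0 section 6.2.1 tests study vaccination number in subjects of all ages, although by schedule only infants have later study doses, so the p-value mixes dose with age; which doses count for an infant with several is also not stated (minor fix)

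*SAP*

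**What the plan says.** SAP V6.0 section 6.2.1 reports adverse events by baseline characteristics in the Safety Set and the Safety per Protocol Set. It analyses each factor by chi-square, or by Fisher's exact test when more than 20% of expected counts fall below 5. Section 8 sets two-sided 0.05. The factors include "Study vaccination number (1, 2, 3, 4" and "Age group (2-23 months, 2-10, 11-18, 19-34, 35-55, 55-64", together with administration site (deltoid and thigh rows) and a split at 18 years. No factor is limited to infants.

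The dosing schedule is in section 3.1. For older subjects: "2 to 55 years of age : MenACWY-CRM is to be administered as a single dose (0.5ml". For those aged 2-23 months, with parental consent, "these subjects may be followed up for 29 days within the surveillance period after subsequent vaccination(s) at the same study site"; they may enter at any point in the series. Section 2.4 has the diary cover "medically attended AEs or SAEs occurring up to Day 29 within the surveillance period after each study vaccination".

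The counting unit is the subject. Section 4.1: "Safety will be assessed after administration of study vaccine in terms of the number and percentage of subjects with". Section 6.2 likewise begins "The number of subjects of AE".

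Section 6.2.3, items 3 and 4, gives by-dose counts and percentages by preferred term for infants aged 2-23 months only, with no test. The latest table shells in the file are those of V4.0. There, Table 2.1.14 has rows 1-4 and a p-value column with no infant limit, Table 3.1.3 has a column per study dose for infants only, Table 1.1.12 counts subjects over rows 1-4, and Table 2.1.8 marks both thigh rows as infant only. Protocol 7.1, printed in the version 1 body, makes all analyses descriptive.

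**The concern.** A p-value over study vaccinations 1 to 4 invites the reader to see an effect of dose. In the pooled population the rows also differ in age. Infants have their own solicited-event list below 6 years (Table 3.1-1 of SAP section 2.4), so an age difference in any-event risk is plausible whatever the dose does. The infants who return for later doses are also counted in more than one row if rows are doses, whereas the chi-square test assumes independent records.

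A second gap follows from the same design. A subject is the unit, but the supplied text does not say which doses count for an infant with several. If an event after any dose counts, an infant has several follow-up windows and an older subject has one. Any factor that separates the two then compares unequal exposure, in a study whose stated objective (SAP section 1) is the safety of a single dose. The nearest rule, in protocol 7.6.3, settles severity and relationship when an event recurs; it does not deal with repeated doses.

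**Working it through.** **The plan's own figures (SAP 2.2).** Evaluable subjects: 3,000 + 600 = 3,600. Enrolment: 3,600 × 1.10 = 3,960, as stated; 3,960 × 0.90 = 3,564, which is within rounding of the approximate 3,600. Older share of study vaccination 1: 3,000/3,600 = 83%.

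**Assumptions.** The documents give neither adverse-event risks nor the number of infants with a second study dose. I assume 10%, 20% or 50% of 600, that is 60, 120 or 300 second doses.

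**Formula.** For rows of size n_i and risk p_i with pooled risk P, the noncentrality is λ = Σ n_i(p_i − P)² / [P(1 − P)]. The chance of p<0.05 is the upper tail of the noncentral chi-square beyond the 5% critical value.

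**Dose test, rows = doses, no dose effect among infants, older risk 30%.** Simplified to two rows (1 df). With infants at 35%, row 1 has risk (3,000 × 0.30 + 600 × 0.35)/3,600 = 30.8%. With 60 second doses, P = (1,110 + 21)/3,660 = 30.9% and λ = 0.48. With infants at 40%, row 1 has risk 31.7%.

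| Second doses | λ, infants 35% | p<0.05 | λ, infants 40% | p<0.05 |
|---|---|---|---|---|
| 60 | 0.48 | 11% | 1.89 | 28% |
| 120 | 0.94 | 16% | 3.71 | 49% |
| 300 | 2.24 | 32% | 8.79 | 84% |

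At equal infant and older risk, λ = 0 and the result is 5%. A simulation in which the same infants appear in both rows (intraclass correlation 0.3) gives 11.0% or 28.5% with 60 second doses, 16.8% or 48.5% with 120, and 4.8-5.0% at equal risk. Age confounding therefore drives the numbers; the repeated infants matter less.

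With all four rows (3 df) and 150/50/25 up to 450/300/200 infants at doses 2/3/4, the pooled test gives 17-52% at 30% against 35%, and 57-99% at 30% against 40%. A test within infants only gives 4.6-5.4% if doses are independent and 1.7-4.2% at intraclass correlation 0.3.

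**Dose test, rows = subjects by number of study doses.** An infant with k doses has k follow-up windows. With equal per-dose risk p and independent doses, the any-event risk is 1 − (1 − p)^k. At p = 0.10 and k = 1 to 4 this is 10%, 19%, 27% and 34% with no dose effect at all.

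**Other 6.2.1 tests if any-dose events count.** Let p be the same per-dose risk at all ages (0.1 to 0.3), s the share of infants with a second dose, and r the between-dose correlation. Two-dose risk: t = 1 − [(1 − p)² + r·p(1 − p)]. Infant risk: (1 − s)p + s·t. For p = 0.3, s = 0.2, r = 0: t = 0.51, and infant risk is 0.8 × 0.3 + 0.2 × 0.51 = 34.2%. Assumed rows: age 600 + 4 × 750; site 1,500/1,500/300/300; 18-year split 2,100 (600 infants and 1,500 older) against 1,500.

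| Factor | r | s = 10% | s = 20% | s = 50% |
|---|---|---|---|---|
| Age group, five rows | 0 | 7-11% | 15-33% | 74-99% |
| Age group, five rows | 0.3 | 6-8% | 10-17% | 42-82% |
| Administration site | 0 | 8-12% | 17-37% | 79-99% |
| Under 18 against 18 and over | 0 | 6-7% | 8-12% | 23-48% |
| Under 18 against 18 and over | 0.3 | 5-6% | 6-8% | 14-27% |

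The six age bands of V6.0, with 40 subjects assumed in the top band, give 7-10%, 14-30% and 71-99% at r = 0. If only first-dose events count, or no infant has a second dose, these tests keep 5%.

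**The case against.** Much can be said for the plan.

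- When infants truly differ from older subjects, the row proportions do differ, and rejecting is right for the hypothesis tested. The dose-test percentages must not be read as false-positive rates. This stands.
- Section 6.2.1 holds crude background-factor tables, and other factors are entangled with age too. True, but study vaccination number is tied to age by the schedule itself, and an infant-only version is easy to produce.
- Section 6.2.3 already gives by-dose results in infants. It does, and soundly, but without touching the 6.2.1 p-value.
- The magnitudes rest on assumed risks and dose counts. Later follow-up needs consent, the same site and time left in the surveillance period, so 50% is an upper scenario. This stands.
- The V6.0 shells and the protocol bodies of versions 2-5 are not in the file, and a counting footnote or an infant limit could be there. This stands, so the gap is one in the supplied text only.

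Three stronger readings are tempting and are not supported. A reader might infer that the SAP names no counting unit; sections 4.1 and 6.2 name the subject, and only the dose rule is missing. A reader might infer that the age tests are invalid as planned; that depends on any-dose counting, which the text does not state, and equal any-event risk across ages is only a reference case because the solicited lists differ. A reader might infer that older subjects can never have a second dose; that holds by schedule, but an off-label repeat dose is excluded only from the per-protocol set, not from the Safety Set.

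**Conclusion.** The point holds as a minor fix. As section 6.2.1 stands, the test of study vaccination number cannot isolate a dose effect. With rows as doses it mixes dose with age and repeats infants; with rows as subjects it compares unequal follow-up. Under the stated assumptions, an age difference of 5 to 10 points alone produces p<0.05 in 11% to 84% of trials, and no age difference gives 5%.

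The second part is conditional. If any-dose events count and some infants have a second study dose, the age-group and administration-site tests are distorted to a similar degree, and the 18-year split less so. The comparison among age bands from 2 years up is not affected.

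A reader might infer that the trial's main safety conclusion is at risk. It is not: the p-values are nominal, and protocol 7.1 (version 1 body) attaches no hypothesis to the primary objective. What changes is the reading of some reported comparisons.

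**What to change.** (a) In 6.2.1, limit the study vaccination number comparison to 2-23 months. Use infants with safety data after that dose as the denominator and show n (%) without a p-value. Add a note that infants may enter mid-series; for that reason, and because infants repeat across doses, a test within infants would still not give a clean dose effect.

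(b) Base all the remaining between-group p-values in 6.2.1, not only those for age, on events after the first study vaccination, one record per subject. State this once as the counting rule. It covers administration site and the 18-year split, and avoids two definitions of a subject with an event in one section.

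(c) Keep the all-dose summaries of adverse events, serious adverse events and deaths, labelled as any study dose, and keep the infant by-dose tables of 6.2.3, so that no safety information is lost.

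The cost is SAP wording, a footnote on the unit and a few table rows; no new data are needed. The downside is that, for an infant who enters mid-series, the first study vaccination is not the first dose of the series.

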2.1 Safety Set

Table 2.1.1 Summary of AE

Safety set	No. subjects with AE n (%)	95% CI† for the percentage of subjects with AE (Lower , Upper)	No. AEs n	No. subjects with ADR n (%)	95% CI† for t percentage o subjects with A (Lower , Upp
Solicited AE (2-23 months)					
Local AE					
Systemic AE					
Solicited AE (2-5 years)					
Local AE					
Systemic AE					
Solicited AE (≥ 6 years)					
Local AE					
Systemic AE					

Safety set	No. subjects with AE n (%)	95% CI† for the percentage of subjects with AE (Lower ,Upper)	No. AEs n	No. subjects with ADR n (%)	95% CI† for the percentage of subjects with ADR (Lower ,Upper)	No. ADR n	Total n (%)
Unsolicited AE							
SAE							
MAAE							
Death							
Total							

† 95% CI will be calculated using the normal approximation.

* Day 1-7: Solicited AE, Unsolicited AE

* Day 1-29: SAE, Death

* Day 8-29: MAAE

Table 2.1.2 Summary of AE by Age (month, year)

Safety Set	No. subjects with AE	No. AEs	Total	p-value
	n (%)	n	n (%)	
2-23 months				X ² -test or Exact test
2-10				
2-5				
6-10				
11-18				
19-34				
35-55				
> 55				
Total				

Table 2.1.3 Summary of AE by Age (month, year)

Safety Set	No. subjects with AE	No. AEs	Total	p-value
	n (%)	n	n (%)	
Solicited AE				X ² -test or Exact test
2-23 months				
2-10				
2-5				
6-10				
11-18				
19-34				
35-55				
> 55				
Solicited Local AE				X ² -test or Exact test
2-23 months				
2-10				
2-5				
6-10				
11-18				
19-34				

Safety Set	No. subjects with AE n (%)	No. AEs n	Total n (%)	p-value
35-55 > 55				
Solicited Systemic AE 2-23 months 2-10 2-5 6-10 11-18 19-34 35-55 ≥56				X ² -test or Exact test
Unsolicited AE 2-23 months 2-10 2-5 6-10 11-18 19-34 35-55 ≥56				X ² -test or Exact test
SAE 2-23 months 2-10 2-5 6-10 11-18 19-34 35-55 ≥56				X ² -test or Exact test
MAAE 2-23 months 2-10 2-5				X ² -test or Exact test

Safety Set	No. subjects with AE n (%)	No. AEs n	Total n (%)	p-value
6-10				
11-18				
19-34				
35-55				
≥56				
ADR				
2-23 months				
2-10				
2-5				
6-10				X ² -test or Exact test
11-18				
19-34				
35-55				
≥56				
Death				
2-23 months				
2-10				
2-5				
6-10				X ² -test or Exact test
11-18				
19-34				
35-55				
≥56				

Table 2.1.4 Summary of AE by Children group

Safety Set	No. subjects with AE n (%)	No. AEs n	Total n (%)	p-value
< 18 years				
≥ 18 years				X ² -test or Exact test
Total				

Table 2.1.5 Summary of AE by Gender

Safety Set	No. subjects with AE n (%)	No. AEs n	Total n (%)	p-value

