2.2 Number of Subjects

A total of approximately 3,960 subjects are planned for enrolment into this study.

Assuming a 10% drop-out rate, this should provide approximately 3,000 evaluable subjects in the cohort 2 to 55 years of age and 600 in the cohort 2 to 23 months of age. This sample size meets the post-licensure requirements of the MFDS to provide continued safety monitoring in the Korean population.

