7.4 Additional Analyses for DDS (Data Disclosure Shell)

- Frequency and percentage by Age group (2-23 months, 2-10, 11-18, 19-64)
- Frequency and percentage by study termination and reason not completed
- Incidence proportion and the number of Non-SAE
- The number of death resulting from AE (frequency and percentage)
- Incidence proportion and number according to the preferred terms of Non-SAE (frequency and percentage)

7.5 Additional Analyses for AE in the Local Product Label (Unsolicited AE Day 1-29)

- Preferred terms of Serious AE/ADR, unexpected AE/ADR will be presented respectively according to the proportion.

	CONFIDENTIAL :	Last Update Date
	THIS DOCUMENT AND INFORMATION CONTAINED HEREIN IS PROPRIETARY TO COMPANY AND IS NOT TO BE DISCLOSED WITHOUT THE WRITTEN PERMISSION OF COMPANY.	20-APR-2018
STATISTICAL ANALYSIS PLAN(V6.0)		

8. Notes

- Each statistical analysis will be carried out with SAS Software version 9.4 or more recent version.
- In the descriptive statistics, mean, SD, minimum, median, and maximum will be calculated for continuous variables, and frequency and percentage for categorical variables.
- Data including sign of inequality such as “ ≥ 20 ”, “ > 20 ” will be excluded from analysis.
- All test statistics will be the results of two-sided tests with the statistical significant level of 0.05.
- The followings shall be included only in re-examination report:
 - Analysis by type of concomitant medications
 - Item ② of paragraph 6.2.3
 - Estimation of 95% confidence interval for incidence proportion of AEs by background factors
 - Paragraph 6.3, 6.4

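### The rule for switching from chi-square to Fisher sets no minimum expected count, so a nearly empty 55-64 age row can leave chi-square in place for uncommon events in the Safety Set

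*SAP*

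**What the plan says.** SAP V6.0 section 6.2.1 tests each baseline characteristic by chi-square and falls back on Fisher under one condition: "If more than 20% of expected frequencies of the cell counts are less than 5". The condition counts the share of small cells only. There is no floor on any single expected count, and no rule for pooling or omitting sparse levels.

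Two of the listed characteristics have more than four levels and include a level that may be nearly empty:

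- "Age group (2-23 months, 2-10, 11-18, 19-34, 35-55, 55-64"), six bands
- "Administration site (left deltoid, right deltoid, left thigh, right thigh, other"), five levels

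Eligibility in section 2.3.1 ends the day before the 56th birthday. Age 55 is therefore eligible, and it falls in both of the last two age bands. Section 8 (Notes) sets the threshold: "All test statistics will be the results of two-sided tests with the statistical significant level of 0.05".

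The footnote to 6.2.1 defines AE as the composite of solicited, unsolicited, medically attended and serious events. Age tests by event type appear in the V4.0 Appendix 1 shells: Table 2.1.3 has separate p-value cells for unsolicited AE, MAAE, ADR and others, with a row above 55 years. The V6.0 shells are not among the documents.

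**The concern.** The chi-square approximation breaks down when a cell's expected count is far below 1, and the fallback exists to catch that. A rule based only on the proportion of small cells catches it in short tables but can miss it in longer ones, because a single sparse row is diluted by the well-filled rows. V6.0 added to 6.2.1 an age band lying almost wholly outside the eligible range, which is the kind of row the rule can miss.

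At stake is a spurious age signal in a regulatory safety report: one ineligible subject with one event could yield a very small p-value that the exact test would not support.

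**Working it through.** **Inputs.** From SAP V6.0: the switch rule, six age bands, five sites, two-sided 0.05, and the sample size in section 2.2. The plan's own total reproduces: 3,000 + 600 = 3,600 evaluable, and 3,600 × 1.1 = 3,960 ("A total of approximately 3,960 subjects are planned for enrolment into this study"). The worked tables use 3,600. The documents give neither event rates nor band sizes, so those below are assumptions, shown over a range.

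**Step 1: when one sparse row triggers Fisher.** A table of R rows by event yes/no has 2R cells. A row with fewer than 5 subjects makes both its cells small, a share of 2/(2R) = 1/R.

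- R = 4: 25%, Fisher used.
- R = 5 (site): 2/10 = 20%, not more than 20%, chi-square kept.
- R = 6 (age): 2/12 = 16.7%, chi-square kept.
- One further small cell: 3/10 = 30% or 3/12 = 25%, Fisher used.

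So chi-square survives in the age table only if every other band expects at least 5 events. At 2% incidence that needs 5/0.02 = 250 subjects per band; at 1% it needs 500.

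**Step 2: size of the statistic.** If the sparse row has one subject with one event and the other rows share the common proportion p, chi-square is about (1 − p)/p on 5 df. Assumed bands 600/500/800/1,300/399/1, where the last row's expected count equals p:

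| Target incidence | Events / 3,600 | Expected count, last row | Chi-square | Chi-square p | Fisher-Freeman-Halton p |
|---|---|---|---|---|---|
| 2% | 73 | 0.020 | 48.3 | 3 × 10⁻⁹ | 0.11 |
| 3% | 109 | 0.030 | 32.0 | 0.000006 | 0.16 |
| 4% | 145 | 0.040 | 23.8 | 0.0002 | 0.21 |
| 10% | 361 | 0.10 | 9.0 | 0.11 | 0.42 |
| 30% | 1,081 | 0.30 | 2.3 | 0.80 | 0.85 |

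Check at 4%: (3,600 − 145)/145 = 23.8. The exact p-values come from 200,000 fixed-margin tables. The 0.001 critical value on 5 df is 20.5, so p < 0.001 from one such event needs p below 1/(1 + 20.5) = 4.65%.

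**Step 3: false positives with no age effect.** Assumed bands 600/500/800/1,300/395 plus m subjects in the last row, 40,000 simulated tables per setting, switch rule applied:

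- m = 1 to 3, incidence 2-5%: chi-square kept in over 99.9% of tables; rejection about 4-10% at 0.05 and 0.4-4% at 0.001.
- m = 1 to 3, incidence 30%: 4-5% at 0.05, no inflation.
- m = 20, incidence 2-5%: 5.3-5.7% at 0.05, little inflation.
- m = 1, incidence 1%: Fisher used in about 94% of tables, because the 395 band expects only 3.95 events.

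**Step 4: site table.** The gap is the same, but V4.0 Table 2.1.8 tests the composite AE only. The 0.001 critical value on 4 df is 18.5, so one event in a one-subject row gives p < 0.001 only if composite incidence is below 1/(1 + 18.5) = 5.1%. At 30% the same pattern gives p of about 0.67.

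**The case against.** The case against is substantial, and most of it narrows the point.

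- **A sparse row does not disable the fallback.** A reader might infer that Fisher can never be reached in these tables. That is not so: a third small cell brings it in, so very rare outcomes such as SAE and death are mostly protected.
- **Section 6.2.1 is written for the composite AE.** If that is common, chi-square is not distorted. The tests by event type rest on the V4.0 shells, whose age rows differ slightly from the V6.0 list (2-5 and 6-10 nested within 2-10).
- **The 55-64 row need not be sparse.** If 55-year-olds are counted there rather than in 35-55, it could be well filled.
- **Only the Safety Set is exposed.** Section 3.1 removes subjects outside the indication from the per-protocol set, and the V4.0 per-protocol age tables have no row above 55.
- **The study is descriptive.** Protocol section 7.1 attaches no null hypothesis to the objective, and no decision hangs on these p-values.
- **The contrast depends on which exact test is used.** A permutation test ordered by the Pearson statistic gives about 0.04 and 0.03 in the 4% and 3% examples, still below 0.05. The figures of about 0.2 and 0.16 belong to Fisher-Freeman-Halton, which extends the Fisher test named in the SAP to larger tables.

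What remains is that the SAP prescribes a test, a fallback and a significance level, and the fallback misses a kind of sparse row that the plan itself lists. Calling the study descriptive does not make a misleading p-value harmless once it is printed.

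**Conclusion.** The point holds in a narrow form. The switch rule lacks a minimum expected count, and in the six-band age table it retains chi-square when a nearly empty 55-64 row is the only sparse one. In the assumed settings (1-3 subjects in that row, incidence 2-5%) the error is at most about twofold at the 0.05 level, but roughly 4- to 40-fold at 0.001.

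This rests on four assumptions: 55-year-olds are counted in 35-55; the other bands each expect at least 5 events; the by-type age tests in the V4.0 shells (unsolicited AE, MAAE, ADR) are still produced; and the incidence of those categories is in the range shown.

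Two stronger readings are tempting. One is that all the baseline p-values are unreliable; the documents do not support this, since tables of four or fewer rows trigger Fisher from one such row and a common composite AE shows no inflation. The other is that the site table is equally at risk; its gap is real, but it matters only if composite incidence, solicited reactions included, is below about 5%. The consequence is a possible spurious subgroup signal in a secondary table, not an error in the primary safety description. Priority is low.

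**What to change.** In SAP 6.2.1, keep the present condition and add a second: the exact test is also used whenever any expected count is below 1. Name it as Fisher-Freeman-Halton, by Monte Carlo where the full computation is too heavy. In the one-subject examples above, this replaces 0.0002 and 0.000006 by about 0.2 and 0.16.

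An equally good alternative is to report the out-of-label age band descriptively and exclude it from the test. Either way, state which band holds 55-year-olds, so that the rows do not overlap.

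The cost is one clause in the SAP and one option in the test code. No data collection or sample size changes.

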Male				X ² -test or Exact test
Female				
Total				

Table 2.1.6 Summary of AE by Past diagnosis

Safety Set	No. subjects with AE n (%)	No. AEs n	Total n (%)	p-value
Yes				X ² -test or Exact test
No				
Total				

Table 2.1.7 Summary of AE by Temperature Location

Safety Set	No. subjects with AE n (%)	No. AEs n	Total n (%)	p-value
Axillary				X ² -test or Exact test
Oral				
Rectal				
Ear				
Total				

Table 2.1.8 Summary of AE by Administration Site

Safety Set	No. subjects with AE n (%)	No. AEs n	Total n (%)	p-value
Left Deltoid				X ² -test or Exact test
Right Deltoid				
Left Thigh (Infant only)				
Right Thigh (Infant only)				
Other				
Total				

Table 2.1.9 Summary of AE by Concomitant medication

Safety Set	No. subjects with AE n (%)	No. AEs n	Total n (%)	p-value
Yes				X ² -test or Exact test
No				
Total				

Table 2.1.10 Summary of AE by Kidney Disorder

Safety Set	No. subjects with AE n (%)	No. AEs n	Total n (%)	p-value
Yes				X ² -test or Exact test
No				
Total				

Table 2.1.11 Summary of AE by Liver disorder

Safety Set	No. subjects with AE n (%)	No. AEs n	Total n (%)	p-value
Yes				X ² -test or Exact test
No				
Total				

Table 2.1.12 Summary of AE by Pregnancy

Safety Set	No. subjects with AE n (%)	No. AEs n	Total n (%)	p-value
Yes				X ² -test or Exact test
No				
Total				

Table 2.1.13 Summary of AE by Number of previous MenACWY

Safety Set	No. subjects with AE n (%)	No. AEs n	Total n (%)	p-value
0				X ² -test or Exact test
1				
2				
3				
Total				

Table 2.1.14 Summary of AE by Study vaccination number

Safety Set	No. subjects with AE n (%)	No. AEs n	Total n (%)	p-value
1				

Safety Set	No. subjects with AE n (%)	No. AEs n	Total n (%)	p-value
2				X ² -test or Exact test
3				
4				
Total				

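### Apart from age (and, untested, dose number in infants), background factors are compared only on any AE, which dilutes differences in medically attended and serious events

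*SAP*

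**What the plan says.** SAP V6.0 section 4.1 sets out the safety assessment as follows: "Safety will be assessed after administration of study vaccine in terms of the number and percentage of subjects with" each of four things, namely solicited AEs (Days 1-7), unsolicited AEs (Days 1-7), medically attended AEs (Day 1 to termination) and SAEs (Day 1 to termination).

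Section 6.2.1 lists twelve background factors: age group, children group, gender, past diagnosis, temperature location, administration site, concomitant medication, kidney disorder, liver disorder, pregnancy, number of previous doses and study vaccination number. One footnote defines the outcome for all of them: "AE includes solicited and unsolicited AE (DAY 1-7), medically attended AE (DAY 1-29) and SAE (DAY 1-29"). Each factor is tested by chi-square, or by Fisher's exact test under the rule that begins "If more than 20% of expected frequencies of the cell counts are less than 5". Section 8 adds: "All test statistics will be the results of two-sided tests with the statistical significant level of 0.05". Section 7.3 describes the output by baseline characteristic only as the incidence proportion and number of AEs.

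The latest table shells supplied are those of V4.0, Appendix 1:
- Table 2.1.3 splits age into solicited, solicited local, solicited systemic, unsolicited, SAE, MAAE, ADR and death, each with a p-value.
- Tables 2.1.4 to 2.1.14, such as "Summary of AE by Gender" and "Summary of AE by Past diagnosis", have one row per factor level for subjects with any AE, and one p-value.
- V6.0 section 6.2.3, items 3 and 4, also asks for SAE, MAAE and other event types by study vaccination number in infants of 2 to 23 months, without a test.

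**The concern.** A subject with one day of mild soreness and a subject admitted to hospital each add one to the same count. If solicited reactions are common, they make up most of the union, and a factor that changes only MAAEs or SAEs shifts the total very little. The comparison then answers who reports anything at all, rather than who needed medical care.

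For factors such as past diagnosis, kidney disorder, liver disorder and pregnancy, the clinically interesting question is the second one. A flat any-AE result could be read as reassurance on endpoints it barely measures.

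**Working it through.** **Sample size in the plan.** SAP V6.0 section 2.2 sets the enrolment target: "A total of approximately 3,960 subjects are planned for enrolment into this study". With 10% lost, the plan expects 3,000 evaluable participants aged 2-55 years plus 600 infants of 2-23 months. Evaluable N = 3,000 + 600 = 3,600, and 3,600 × 1.10 = 3,960, which reproduces the stated enrolment. (3,960 × 0.90 = 3,564; the 1% difference does not matter here.) I use N = 3,600 and two-sided 0.05. The plan states no power for any background-factor comparison.

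**Assumed inputs, none of them in the documents.**
- s: proportion with an AE other than an MAAE, 20% to 60%.
- m: MAAE proportion in the reference level, 2% to 15%, doubled in the other level.
- f: prevalence of the factor, 50% down to 1%.
- Independence of MAAEs and other AEs, and s equal in both levels.

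**Formulas.** Composite proportion: P = 1 − (1 − s)(1 − m). Power ≈ Φ[(d − 1.96·SE0)/SE1], where d is the difference in proportions, SE0 the pooled and SE1 the unpooled standard error.

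**Worked case, s = 40%, m = 5% v 10%.** Composite: 1 − 0.60 × 0.95 = 43.0% v 1 − 0.60 × 0.90 = 46.0%. The 5-point MAAE difference has shrunk to 3 points, on an outcome with much larger variance.
- 50/50 factor (1,800 v 1,800), composite: SE0 = SE1 = 0.0166; (0.030 − 0.0325)/0.0166 = −0.15; power 44%. MAAE alone: SE0 = 0.0088, SE1 = 0.0087; (0.050 − 0.0172)/0.0087 = 3.8; power >99%.
- 10% factor (3,240 v 360), composite: SE0 = 0.0275, SE1 = 0.0277; (0.030 − 0.0540)/0.0277 = −0.87; power 19%. MAAE alone: SE0 = 0.0127, SE1 = 0.0163; (0.050 − 0.0248)/0.0163 = 1.55; power 94%.

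**Other settings** (power to see MAAEs double):

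| Factor | s | m | Composite | MAAE alone |
|---|---|---|---|---|
| 50/50 | 20% | 5% | 78% | >99% |
| 50/50 | 30% | 5% | 59% | >99% |
| 50/50 | 60% | 5% | 24% | >99% |
| 50/50 | 40% | 2% | 11% | 94% |
| 50/50 | 40% | 3% | 19% | 99% |
| 50/50 | 40% | 8% | 82% | >99% |
| 20% | 40% | 5% | 31% | >99% |
| 10% | 50% | 5% | 15% | 94% |
| 5% | 40% | 5% | 12-13% | 77% |
| 1% | 40% | 5% | 7% | 33% |

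At 1% prevalence (36 subjects) the normal approximation is rough, but the conclusion that power is low is safe.

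At s = 40%, composite power falls below 50% when m is under about 5.5% (50/50 factor), 6.8% (20%), 9.1% (10%) or 12.5% (5%). Over a grid of f = 50, 20, 10 and 5%, s = 20-60% and m = 2-15%, 74 of 120 settings have power below 50%.

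**Overlap** (50/50, s = 40%, m = 5%). If MAAEs occur only in subjects with no other AE, the composite is 45% v 50% and power is 85%. If an MAAE is half as likely to be a subject's only AE as under independence, it is 41.5% v 43.0% and power is 15%.

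**The case against.** Several points on the other side are sound.

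- A reader might infer that a doubling of MAAEs would usually be missed, whatever the factor. The documents do not support that: they give no event rates, prevalences or overlap, and in 46 of the 120 grid settings composite power is 50% or more. For a balanced factor with m = 8%, it runs from 52% to 99% as s falls from 60% to 20%.
- A reader might also infer that these tables are the only planned look for vulnerable subgroups. They are not. Age, the one stratification Protocol section 7.6 requires, is split by endpoint in the V4.0 shells, and children group is a coarser cut of age. Event types are shown by dose number in infants. Protocol section 7.6.3 promises by-subject listings and separate summaries of SAEs and related MAAEs.
- No V6.0 appendix is supplied. V4.0 section 6.2.1 carries the same pooled definition, yet its shells split age, so the V6.0 text alone does not prove what every V6.0 table contains.
- Participants must be in good health, so kidney disorder, liver disorder and pregnancy may be rare. For such factors, low numbers limit detection whichever outcome is used.
- If the factor also raised other AEs by 5 points (30% to 35%, or 50% to 55%), composite power at 10% prevalence and MAAE 5% v 10% would be 85% or 72%. A positive result would still not show that MAAEs had moved.
- Protocol section 7.1 calls the study descriptive, and copying Table 2.1.3 in full would add about 5 endpoints × 11 factors × 2 analysis sets = 110 tests.

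These limit the size of the claim and the form of the remedy. They do not explain why four separate endpoints are merged for the factor comparisons. That the study is descriptive favours showing the endpoints: section 6.2.1 already attaches a test, and attaches it to the least specific outcome.

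**Conclusion.** The concern holds in a conditional form. As written, V6.0 sections 6.2.1 and 7.3 compare background factors on a pooled outcome. The only exceptions visible are age, known from the V4.0 shells, and study vaccination number in infants, untested.

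With N = 3,600, independence, an MAAE proportion of about 5% or less and 40% or more of subjects having another AE, a doubling of MAAEs would be missed more often than not on the composite, although MAAEs analysed alone would usually show it unless the factor is uncommon. For balanced factors with more frequent MAAEs or fewer other AEs, the composite could detect it. Near 1% prevalence neither analysis has much power, but separate counts would at least make an individual SAE in a small group visible in the factor table.

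This is a worthwhile change to the analysis plan. It does not undermine the overall safety summaries.

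**What to change.** In V6.0 sections 6.2.1 and 7.3, for each factor other than age, add descriptive rows for subjects with any solicited AE, unsolicited AE, MAAE, SAE and ADR, as n and % with 95% CI. Use the row layout of V4.0 Table 2.1.3 without its p-value column, and state that the column is dropped. Take the event windows from V6.0 (MAAE Day 1-29), not from the V4.0 shells, which used Day 8-29. Keep any AE as a summary row. Section 8 places confidence intervals by background factor in the re-examination report only; the new intervals can follow that rule.

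The cost is more table pages in both analysis sets. No new data are needed and no tests are added.
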